Annex 4. Baseline Survey Questionnaire (VCT)

Baseline Survey Questionnaire

Introduction

Thank you for your willingness to participate in this study and to answer this simple questionnaire. Your participation is greatly valued. Allow us to provide some more information regarding the survey.

Firstly, this study is part of a national study in evaluating the most appropriate method for HIV testing for female sex workers who are at least 18 years of age, have never been tested for HIV and have not undergone HIV testing in the last 6 months but would like to receive HIV blood testing at this time.

Secondly, your participation and personal information will be kept **confidential**. Only the research team will know you, and you will not be writing your name or any identifying information explicitly on this questionnaire.

Additionally, only the research team will know your answer. Each questionnaire has been given a code, such that your personal details will be safe and can only be accessed by the research team.

Thirdly, the findings in this study will be presented as a collective result, such that personal information will not be presented, including yours.

Fourthly, you may refuse to answer the questions given, however we will greatly appreciate if you answer all the questions, as it will assist us in generating better results.

Should you have doubts regarding a particular question or certain words in this questionnaire, do not hesitate to **contact us (at OW/PE's phone number: _____)** for further explanation. There is no right or wrong answer, please provide that answer that you consider most accurate.

Are you ready to begin?

Note: directly inputted to the system

Baseline Survey for All Participants (Blood testing at healthcare facility and HIV self-testing)

Participant Code Number		
Name of OW/PE (assisted)		
1.	Please write your full name or initials	
2.	What is your date of birth?	Day: ___ Month: __ Year: ____
3.	Your age is years old
		1. Did not attend school

4.	What was the education level you last received?	2. Did not complete elementary school/ equivalent
		3. Completed elementary school/equivalent
		4. Did not complete middle school/equivalent
		5. Completed middle school/equivalent
		6. Did not complete high school/equivalent
		7. Completed high school/equivalent
		8. Ever attended/completed bachelor studies
5.	What is your current marital status?	1. Never married
		2. Married (including unofficial marriages)
		3. Separated
		4. Widowed
		5. Divorced
6.	Do you have a consistent partner (boyfriend/husband) in the past month?	1. Yes
		2. No
7.	What was your age when you first engaged in sex with a client? (years of age)
8.	What is the approximate number of clients you had in the past 7 days? (people)
9.	How often do you use condom when engaging in sex with your clients in the past month?	1. Always
		2. Very frequent
		3. Often
		4. Sometimes
		5. Never

10.	Where do you usually look for or find your client (potential client)? (CHOOSE ALL THAT APPLY)	a. Location
		b. Streets
		c. Spa
		d. Café
		e. Karaoke
		f. Salon
		g. Bar
		h. Massage parlour
		i. On-line (web application, SMS, social media)
		j. Others, _____

11.	Have you ever experienced symptoms such as abnormal vaginal discharge, itching, or pain during sexual intercourse?	1. Yes	
		2. No	
		3. Not sure	
12.	Have you ever been diagnosed with a sexually transmitted infection by a doctor in the past six months?	1. Yes	
		2. No	
		3. Not sure	
13.	When was the last time you took an HIV test?	1. Never 2. 6 to 12 months 3. more than one year to two years 4. more than two years	
14.	In the past one year, have you ever received an HIV test offer?	1. Yes → P.15 2. No → P.17	
15.	Did you agree or decline to undergo the HIV testing?	1. Agree 2. Decline → P.16	
16.	Why did you decline the HIV testing at that time? (Choose all that apply)		
	a. Afraid to have blood sample taken	1. Yes	2. No
	b. Fear of needle/injection	1. Yes	2. No
	c. Afraid of receiving a positive result	1. Yes	2. No
	d. Afraid that others might know about the results	1. Yes	2. No
	e. Uncomfortable while undergoing testing (crowd, time, etc)	1. Yes	2. No
	f. Live far from community health centre/hospital/clinic	1. Yes	2. No
	g. Embarrassed to undergo testing at the clinic	1. Yes	2. No
	h. Perceive to have low risk	1. Yes	2. No
	i. Other reasons, please mention	_____	

17.	Where did you hear about HIV self-testing? (Choose all that apply)		
	a. Staff/NGO/Foundation	1. Yes	2. No
	b. Friends	1. Yes	2. No
	c. Someone at the workplace (madam, security, etc.)	1. Yes	2. No
	d. Internet	1. Yes	2. No
	e. Social media	1. Yes	2. No

	f. Chain messages (broadcasted messages)	1. Yes	2. No
	g. Others, _____	1. Yes	2. No

QUESTIONS ON STIGMA

No	Question	Extremely Disagree	Disagree	Agree	Extremely Agree
	Personalized stigma				
1	Others will avoid touching me if I am infected with HIV				
2	I am worried that my family/friends/partner/husband/boss will end their relationship/contact with me if I am infected with HIV				
3	I am worried that I will lose my friends if I am infected with HIV				
	Concerns with Revealing Status				
4	Revealing to others that I am infected with HIV will pose a risk to me				
5	I have to conceal my status if I am infected with HIV				
6	I might have to be extremely careful to whom I reveal that I am infected with HIV				
	Concerns regarding public attitude				
7	I am afraid that I will be treated like an unwanted person if I am infected with HIV				
8	Most people believe that those infected with HIV are dirty				
9	Most people feel uncomfortable being around people living with HIV				
	Negative Self Perception				
10	I feel at fault if I am infected with HIV				
11	Others attitude towards HIV will worsen my feelings if I am infected with HIV				

12	I feel that I am not as good as others if I live with HIV				
----	-----------------------------------------------------------	--	--	--	--

FINAL

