A short baseline survey will be conducted at the time of initial outreach contact with FSW during the study period. The purpose of the baseline survey is to collect background information on FSW that may be used to assess whether FSW with different characteristics are more or less amenable to community HIV screening and HIV testing at health facilities. An application will be developed so that the survey can be completed and submitted to a server using mobile phones PL/PE/FSW. The following basic information will be gathered (see draft questionnaires for the baseline and post-test surveys in the annex of this protocol).

- Name (full name/initial)
- Age
- Date of birth

- Test Kit ID Number
- Education
- Marital status
- Age at initiation of sex work
- Number of clients last seven (7) days
- Methods of clients' recruitment (fixed facility, street, internet, online platform)
- Consistency of condom use
- Ever been tested for HIV
- When last time tested
- Ever been diagnosed with an STI (other than HIV)

In addition to these questions, FSW will be asked twelve (12) questions in the short version of anticipated HIV stigma scale (Reinius et al., 2017) designed to measure the extent to which participants anticipated negative intrapersonal and interpersonal consequences were they to contract HIV in the future. During data analysis, we will assess the ability of an index constructed from the data items collected to predict which FSW presented at health facilities for formal HIV testing. This will provide an estimate of the impact of anticipated stigma on HIV testing among FSW in Indonesia.

2. Post-test Survey

A short post-test survey will be conducted after the test has been taken. The purpose of post-test survey is to collect information of the experience of clients using the test kit and to record the test result. Some inquiries will be presented on a scale of 1-5, some inquiries will have binary answers (Yes/No, Reactive/Non-Reactive). The following inquiries will be made:

- The clarity of information being provided (flier or short video), on a scale of 1-5
- The easiness of test procedure, on a scale of 1-5
- Perceived accuracy of the test result, on a scale of 1-5
- The quality of response by the assigned contact person/hotline, on a scale of 1-5
- Clients' acceptance/perception towards the study procedure
- The likelihood of clients to recommend their peers to take the test, on a scale of 1-5
- Test result

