In the event that participants' data are collected by paper, a procedure to upload the data into the established online system will be developed. Each data manager in the IUs needs to conduct the procedure regularly. This is to ensure that all data are being captured thoroughly.

F. DATA ANALYSES

The data analyses to be undertaken will be directed to addressing the research questions laid out at the beginning of the protocol and statistical tests appropriate to each specific analysis will be performed to inform the interpretation of results. The specific steps in the data analysis will be as follows:

1. Compare the characteristics of FSWs who receive self-testing and blood testing.

2. Compare the characteristics of FSWs who receive assisted and unassisted self-testing.
3. Compare proportion of FSWs taking confirmatory test out of those who receive the test in the assisted and unassisted self-testing.
4. Compare the proportion of FSWs who receive HIV test out of those who got offered for the test (including self-testing) in the intervention group with proportion of FSWs who receive HIV test in the control group.
5. Compare the proportion of FSWs taking confirmatory test (including self-testing) out of those receive the test in intervention groups and control group.
6. Compare the proportion of HIV positive in the assisted, unassisted (intervention) and HIV positive in the control group.
7. Compare the proportion of ART initiation in the assisted, unassisted (intervention) and the control group.
8. Calculate the cascade of HIV testing and treatment.
9. Compare stigma scores and FSWs who went to a health facility for HIV testing between assisted, unassisted group.
10. Compare the HIV and STI risk behaviors between assisted and unassisted group.

G. CONTINGENCY STUDY DESIGN

Should the OraQuick® test kits not become available in sufficient time to conduct a full-scale cRCT, a smaller-scale study will instead be undertaken. The purpose of the smaller study is the same as the cRCT described above, and the same protocol described above will be implemented. But the comparison is achieved targets between before and after intervention – there will be no comparison districts. The study will be undertaken in three (3) districts. The three districts will be selected from different parts of Indonesia, and they are: Kota Bandung (west part of Indonesia), Kota Denpasar (central part of Indonesia), and Kota Makassar (center-east part of Indonesia).

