Annex 1. Flowchart of Routine Data Recording

Annex 2. Eligibility Form

Eligibility Participants Form for Intervention

To be completed by PL/PE during FSW outreach

These checklists are to be completed by PL/PE during FSW outreach to assess the eligibility of FSW to participate in this study. If questions number 1-7 is answered “Yes”, then participant is eligible for the study. If question number 8 is answered “Yes”, then participant is not eligible for the study, but eligible for “blood test study in health facility”.

No	Criteria inclusion	Yes	No
1	Female, aged 18 years old or more		
2	Admit having transactional sex (vaginal, oral, or anal) at least once within the last one month		
3	Have never had any HIV test taken within the last 6 months		
4	Self-reported HIV Negative OR HIV status unknown		
5	Agreed to participate in this study		
6	Not currently participating in any other HIV prevention study		
7	After being offered for HIV testing in health facility, participant stated: A. Agree for HIV testing in health facility* B. Not agree for HIV testing in health facility**		

Note:

* Use information form for VCT

** Use information form for OFT

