6.	Do you have a consistent partner (boyfriend/husband) in the past month?	3. Yes
		4. No
7.	What was your age when you first engaged in sex with a client? (years of age)
8.	What is the approximate number of clients you had in the past 7 days? (people)
9.	How often do you use condom when engaging in sex with your clients in the past month?	6. Always
		7. Very frequent
		8. Often
		9. Sometimes
		10. Never

10.	Where do you usually look for or find your client (potential client)? (CHOOSE ALL THAT APPLY)	k. Location
		l. Streets
		m. Spa
		n. Café
		o. Karaoke
		p. Salon
		q. Bar
		r. Massage parlour
		s. On-line (web application, SMS, social media)
		t. Others, _____
11.	Have you ever experienced symptoms such as abnormal vaginal discharge,	4. Yes
		5. No
		6. Not sure

	itching, or pain during sexual intercourse?	
12.	Have you ever been diagnosed with a sexually transmitted infection by a doctor in the past six months?	4. Yes
		5. No
		6. Not sure
13.	When was the last time you took an HIV test?	5. Never 6. 6 to 12 months 7. more than one year to two years 8. more than two years
14.	In the past one year, have you ever received an HIV test offer?	3. Yes → P.15 4. No → P.17
15.	Did you agree or decline to undergo the HIV testing?	3. Agree 4. Decline → P.16
16.	Why did you decline the HIV testing at that time? (Choose all that apply)	
	j. Afraid to have blood sample taken	3. Yes 4. No
	k. Fear of needle/injection	3. Yes 4. No
	l. Afraid of receiving a positive result	3. Yes 4. No
	m. Afraid that others might know about the results	1. Yes 2. No
	n. Uncomfortable while undergoing testing (crowd, time, etc)	3. Yes 4. No
	o. Live far from community health centre/hospital/clinic	3. Yes 4. No
	p. Embarrassed to undergo testing at the clinic	3. Yes 4. No
	q. Perceive to have low risk	3. Yes 4. No
r. Other reasons, please mention	_____	

17.	Where did you hear about HIV self-testing? (Choose all that apply)	
	h. Staff/NGO/Foundation	3. Yes 4. No
	i. Friends	3. Yes 4. No
	j. Someone at the workplace (madam, security, etc.)	3. Yes 4. No
	k. Internet	3. Yes 4. No
	l. Social media	3. Yes 4. No
	m. Chain messages (broadcasted messages)	3. Yes 4. No
	n. Others, _____	1. Yes 2. No

STIGMA QUESTION

No	Question	Extremely Disagree	Disagree	Agree	Extremely Agree
	Personalized stigma				
1	Others will avoid touching me if I am infected with HIV				

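### Baseline items 14-16 do not exclude the facility-test offer the study has just made, and item 13 has no code for a test under 6 months ago

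*Combined protocol and SAP*

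**What the plan says.** Sections B.1 and C.1 have the blood test at a health facility offered first, with self-screening offered to women who decline it. The answer is written on the eligibility form (Annex 2 item 7: "After being offered for HIV testing in health facility, participant stated"). Accepters are routed to the VCT paperwork and refusers to the OFT paperwork. Section E.1 places the baseline survey at the initial outreach contact.

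The survey items are the same in Annex 4 (VCT) and Annex 6 (OFT):
- Item 13, date of last test. The codes are "1. Never 2. 6 to 12 months 3. more than one year to two years 4. more than two years" in Annex 4 and "5. Never 6. 6 to 12 months 7. more than one year to two years 8. more than two years" in Annex 6.
- Item 14: "In the past one year, have you ever received an HIV test offer". A woman who answers No skips to item 17.
- Item 15: "Did you agree or decline to undergo the HIV testing".
- Item 16, for those who declined: "Why did you decline the HIV testing at that time", followed by a list of reasons.

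Section E.1 gives the survey's purpose as to "assess whether FSW with different characteristics are more or less amenable to community HIV screening and HIV testing at health facilities". The first step in Section F is to "Compare the characteristics of FSWs who receive self-testing and blood testing". Section B.3 requires no HIV test in the last 6 months, and Annex 2 item 3 asks about this directly.

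**The concern.** The survey is meant to show what distinguishes women who take self-screening from those who take a facility test. Whether a woman has been offered a test before, whether she refused and why are natural characteristics to examine. On the face-to-face route, though, every woman has received an offer within the past year by the time she reaches item 14, because she received one minutes earlier. Her answer to that offer also put her in the group being compared. If some women report on it, an association between past refusal and self-testing appears from the order of the forms alone. Once the answers are in, they cannot be separated.

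Item 13 raises a different question. It asks when a woman last tested, but it has no truthful answer for a woman who tested within 6 months and was let through the eligibility screen in error. The survey therefore gives no second look at a criterion that rests on self-report.

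**Working it through.** **Order of events, by route**

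| Route | Facility test offered before the survey? | Source |
|---|---|---|
| Face to face, accepts facility test | Yes; VCT form | B.1, C.1, E.1, Annex 2 item 7 |
| Face to face, refuses, then self-screens | Yes; OFT form | B.1, C.1, E.1, Annex 2 item 7 |
| Online link | Not clearly; the list for the unassisted approach puts the baseline survey before agreement to a facility test | B.1, E.3 |

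**Size of the artefact in items 14-15.** The plan states no figure to reproduce, so what follows is an illustration with assumed inputs:
- q = share of face-to-face women who count today's offer and answer item 15 about it.
- r = share with a real offer earlier in the past year.
- d = share who really refused an earlier offer.

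All three are taken as equal in the VCT and OFT groups, so there is no true difference in history.

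*Among all women*, the share recorded as having declined in the past year is:
- OFT: q + (1 - q)d
- VCT: (1 - q)d
- Difference: q. This is 10 points at q = 0.10 and 50 points at q = 0.50, whatever d is.

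*Among women who reach item 15*, a share q + (1 - q)r answers it. The contribution from earlier offers is the same in both groups and cancels, so the VCT-minus-OFT difference in agreeing is q / (q + (1 - q)r):

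| q | r = 1 | r = 0.5 | r = 0.25 |
|---|---|---|---|
| 0 | 0 | 0 | 0 |
| 0.10 | 10 points | 0.10/0.55 = 18 points | 0.10/0.325 = 31 points |
| 0.50 | 50 points | 0.50/0.75 = 67 points | 0.50/0.625 = 80 points |
| 1 | 100 points | 100 points | 100 points |

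*Face to face against online, item 14.* If online women had no facility offer before the survey, the recorded shares are q + (1 - q)r and r. The difference is q(1 - r). At r = 0.5 it is 5 points for q = 0.10 and 25 points for q = 0.50.

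*Item 16.* Among OFT women, reasons for today's refusal are pooled with reasons for earlier ones. VCT women accepted today, so they can only report earlier refusals. The two lists of reasons would then describe different events.

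If the items exclude today's offer, q = 0 and every difference above is 0.

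**Item 13.** The codes in both annexes run from never tested to 6 months or longer ago. A woman tested two months ago who passed Annex 2 item 3 must choose a wrong code or skip. Two other records bear on this. E.3 row 1 counts women at least 6 months since their last test, in both arms. E.4 matches kit ID to the temporary FSW ID, which detects repeat participation in the study but not a recent test elsewhere.

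**The case against.** The wording is ambiguous rather than wrong. Item 16 asks about refusal in terms that point back to another occasion, and many women would take the block to mean earlier offers. This stands as far as it goes: q may be small. But the pointer appears only in item 16, after items 14 and 15 have been answered, and the listed reasons (blood sample, needle, distance, embarrassment at the clinic) fit a facility test refused minutes before.

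The link to the analysis is also loose. The variable list in E.1 names ever tested and when last tested, but not offers, refusals or reasons. Section F names no analysis of items 14-16, and no primary objective uses them. That limits the stakes. It does not remove the point, because Section F step 1 compares unspecified characteristics and these items are collected as such. E.1 also calls the questionnaires drafts, which makes the change easy.

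On item 13, the eligibility form already asks about a recent test, and a woman who misstated it in order to enter has little reason to correct herself shortly afterwards. This also stands. The added code would mainly catch honest mistakes.

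A reader might infer that undetected recent testers inflate the testing proportion in the intervention arm, using Tables 4 and 5: 6,433 tests per semester and 36,979 women reached per year in the 15 intervention districts, a ratio of 17.4%. The documents do not support that step. The ratio sets a half-year count of tests against a full-year count of women, so it is not the share tested within 6 months at contact. The rates at which such women enter and then test are not given either.

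**Conclusion.** The point holds as a defect in the questionnaire, aligned with the groups compared in Section F step 1. Its size depends on q, which the documents do not give. It is zero only if no woman counts today's offer. On the assumptions shown, even q = 0.10 gives 10 points among all women and 10 to 31 points among those reaching item 15. Item 14 may also differ between the face-to-face and online routes.

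Three stronger readings should be avoided:
- That items 14-15 simply reproduce group membership. This is the extreme q = 1, which needs every woman to answer about today's offer.
- That the artefact carries into Section F step 2 (assisted against unassisted). Face-to-face women in both of those groups refused the facility test, so it does not arise between them. Only women from the online link could introduce a difference.
- That women who retested within 6 months are invisible. Annex 2 item 3 screens for them. What is missing is a consistency check on those who pass that self-report in error.

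No effect on the primary testing proportions is shown.

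**What to change.** In Annexes 4 and 6:
1. Reword items 14-16 to refer to offers made *before today's offer*, within the past 12 months.
2. Add *Less than 6 months ago* to item 13. Report how many women choose it, by arm and route where collected. Leave them out only in a sensitivity analysis, unless the same item is collected and applied in both arms. The documents do not clearly use this survey in comparison districts (Annex 2 is headed as the form for the intervention), so excluding women from the main proportions could fall on one arm only.
3. Optionally, add to Annex 6 one item on why today's facility test was refused, with the same reason list, and do not show it to online women who had no such offer.

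The cost is slightly longer wording and one more response code, plus one extra question if the optional item is taken up. It is cheapest before the survey application is built, because mixed answers cannot be separated afterwards.

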Annex 5. VCT Test Confirmation and Result Form

FOLLOW-UP PARTICIPANT WHO CHOOSE TO PERFORM HIV BLOOD TEST AT HEALTH FACILITY

1	If participant agreed to perform HIV blood test in health facility, did she really go for it? (Needed to be validated at health facility)	1. Yes	2. No
2	Test result	1. Reactive	2. Non-reactive

FINAL

Annex 6. Baseline Survey Questionnaire (OFT)

Introduction

Thank you for your willingness to participate in this study and to answer this simple questionnaire. Your participation is greatly valued. Allow us to provide some more information regarding the survey.

Firstly, this study is part of a national study in evaluating the most appropriate method for HIV testing for female sex workers who are at least 18 years of age, have never been tested for HIV and have not undergone HIV testing in the last 6 months but would like to receive HIV blood testing at this time.

Secondly, your participation and personal information will be kept **confidential**. Only the research team will know you, and you will not be writing your name or any identifying information explicitly on this questionnaire.

Additionally, only the research team will know your answer. Each questionnaire has been given a code, such that your personal details will be safe and can only be accessed by the research team.

Thirdly, the findings in this study will be presented as a collective result, such that personal information will not be presented, including yours.

Fourthly, you may refuse to answer the questions given, however we will greatly appreciate if you answer all the questions, as it will assist us in generating better results.

Should you have doubts regarding a particular question or certain words in this questionnaire, do not hesitate the **contact us (at OW/PE's phone number: _____)** for further explanation. There is no right or wrong answer, please provide that answer that you consider most accurate.

Are you ready to begin?

Note: directly inputted to the system

Baseline Survey for All Participants (Blood testing at healthcare facility and HIV self-testing)

Participant Code Number		
Name of OW/PE (assisted)		
1.	Please write your full name or initials	
2.	What is your date of birth?	Day: ___ Month: __ Year: ____
3.	Your age is years old
4.	What was the education level you last received?	9. Did not attend school
		10. Did not complete elementary school/ equivalent
		11. Completed elementary school/equivalent

		12. Did not complete middle school/equivalent
		13. Completed middle school/equivalent
		14. Did not complete high school/equivalent
		15. Completed high school/equivalent
		16. Ever attended/completed bachelor studies
5.	What is your current marital status?	6. Never married
		7. Married (including unofficial marriages)
		8. Separated
		9. Widowed
		10. Divorced
6.	Do you have a consistent partner (boyfriend/husband) in the past month?	3. Yes
		4. No
7.	What was your age when you first engaged in sex with a client? (years of age)
8.	What is the approximate number of clients you had in the past 7 days? (people)
9.	How often do you use condom when engaging in sex with your clients in the past month?	6. Always
		7. Very frequent
		8. Often
		9. Sometimes
		10. Never

10.	Where do you usually look for or find your client (potential client)? (CHOOSE ALL THAT APPLY)	k. Location
		l. Streets
		m. Spa
		n. Café
		o. Karaoke
		p. Salon
		q. Bar
		r. Massage parlour
		s. On-line (web application, SMS, social media)
		t. Others, _____
11.	Have you ever experienced symptoms such as abnormal vaginal discharge,	4. Yes
		5. No
		6. Not sure

	itching, or pain during sexual intercourse?	
12.	Have you ever been diagnosed with a sexually transmitted infection by a doctor in the past six months?	4. Yes
		5. No
		6. Not sure
13.	When was the last time you took an HIV test?	5. Never 6. 6 to 12 months 7. more than one year to two years 8. more than two years
14.	In the past one year, have you ever received an HIV test offer?	3. Yes → P.15 4. No → P.17
15.	Did you agree or decline to undergo the HIV testing?	3. Agree 4. Decline → P.16
16.	Why did you decline the HIV testing at that time? (Choose all that apply)	
	j. Afraid to have blood sample taken	3. Yes 4. No
	k. Fear of needle/injection	3. Yes 4. No
	l. Afraid of receiving a positive result	3. Yes 4. No
	m. Afraid that others might know about the results	1. Yes 2. No
	n. Uncomfortable while undergoing testing (crowd, time, etc)	3. Yes 4. No
	o. Live far from community health centre/hospital/clinic	3. Yes 4. No
	p. Embarrassed to undergo testing at the clinic	3. Yes 4. No
	q. Perceive to have low risk	3. Yes 4. No
r. Other reasons, please mention	_____	

17.	Where did you hear about HIV self-testing? (Choose all that apply)	
	h. Staff/NGO/Foundation	3. Yes 4. No
	i. Friends	3. Yes 4. No
	j. Someone at the workplace (madam, security, etc.)	3. Yes 4. No
	k. Internet	3. Yes 4. No
	l. Social media	3. Yes 4. No
	m. Chain messages (broadcasted messages)	3. Yes 4. No
	n. Others, _____	1. Yes 2. No

STIGMA QUESTION

No	Question	Extremely Disagree	Disagree	Agree	Extremely Agree
	Personalized stigma				
1	Others will avoid touching me if I am infected with HIV				
2	I am worried that my family/friends/partner/husband/boss will end their relationship/contact with me if I am infected with HIV				
3	I am worried that I will lose my friends if I am infected with HIV				
	Concerns with Revealing Status				
4	Revealing to others that I am infected with HIV will pose a risk to me				
5	I have to conceal my status if I am infected with HIV				
6	I might have to be extremely careful to whom I reveal that I am infected with HIV				

